2.13. Subjects and sample size

Population. Adult healthy subjects.

Sample size. It is required to enroll 54 subjects with a 95% of level of confidence and 80% level of power.

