6.2. Design and comparator

Experimental, randomized and controlled study with the usual technique of inserting a venipuncture catheter until now. Incomplete clinical trial, blind to third parties, in healthy volunteers, which consists of three arms, in which they are intervened and the comparator is applied.

Three interventions are established and a common comparator for all of them. Interventions:

1. Application of dry topical heat.
2. Application of high stagnation pressure.

3. Application of dry topical heat and high stagnation pressure. That is, the combination of the previous two.

Comparator:

1. Usual clinical practice, until now

Therefore, all individuals will be subjected to one of the three interventions and the comparator, whose sequence corresponds to the two periods established by the clinical trial of bioequivalence.

Therefore, all individuals will be subjected to one of the three interventions and the comparator, whose sequence corresponds to the two periods established by the clinical trial of bioequivalence.

It is understood that it is a crossover clinical trial because each subject is exposed to an intervention, and it is their own control; it is exposed to the comparator, whose purpose is to reduce the intraindividual variability and accentuate the effectiveness of the intervention per se. It is an incomplete crossing because it is not possible to subject each individual to the three interventions and it must be only one per random assignment. This impossibility could be supported by the low frequency of clinical trials of four periods carried out in the accessible environment.

In this way, any of the interventions assigned to it can be compared with the current procedure for antebrachial venous cannulation

6.3. Random assignment of interventions.

The intervention and the sequence of application of the intervention with the comparator will be randomly assigned.

They will be assigned with sealed envelopes where inside the corresponding intervention to be applied, the comparator and the corresponding sequence will be detailed. Emerging the following options:

1. CA-> C. Topical first period heat. Comparator in the second period.
2. C-> CA. Comparator in the first period. Topical heat in the second period.
3. P-> C. High pressure in the first period. Comparator in the second period.
4. C-> P. Comparator in the first period. High pressure in the second period.

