14. STATISTICAL ANALYSIS PLAN

14.1. Main analysis

14.1. 1. Definition of variables

Primary variable

Successful venipuncture at the first attempt. Dichotomous qualitative variable. Success / Failure

Secondary variables

Successful venipuncture frequency. Discrete quantitative variable. (1,2,3,4)

Visual intensity of hemolysis. Discrete quantitative variable. It is measured in stadiums.

Scale of expressed pain intensity (VAS). Discrete quantitative variable.

Scale skin types Fitzpatrick. Discrete quantitative variable.

Ingestion of liquids (less than 500 ml) in the last 6-8h prior to cannulation. Discrete quantitative variable (measured in glasses); it will be transcribed continuously for statistical analysis.

Affiliation of individuals

Respected fasting of 6-8 hours. Dichotomous qualitative variable.

Age. Quantitative variable continues.

Sex. Dichotomous qualitative variable.

Race. Discrete quantitative variable. 1 -> Caucasian 2 -> Black 3 -> Asian 4 -> Latin

BP. Continuous quantitative variable.

HR. Continuous quantitative variable.

T. Continuous quantitative variable.

BMI Continuous quantitative variable.

14.1. 2. Sample size calculation

The sample calculation is performed with the GRANMO calculator (63). It assumes a random risk (alpha) of 5% and a statistical power (beta) of 80%; for which it is tried to prove the veracity of the null hypothesis, of bilateral type.

That is, the risk of rejecting the null hypothesis when this is true is 5%, and the probability of not rejecting it being false is 20%.

In the literature, the success of peripheral intravenous canals was recorded in the first attempt, using the usual technique, in 74% of the cases (55). Currently, a proportion of peripheral intravenous cannulation has been registered at the first attempt of 73%, in an ultrasound ecoguided manner (33). In relation to the second successful attempt, in the usual clinical practice it amounts to 92% of the cases and, in the ultrasound ecoguided to 91% (33.55).

For the present work we intend to achieve a 95% success rate in antebrachial venous cannulation at the first attempt. Thus, overcome with one of the alternative methods proposed in this study the cumulative proportion of the second attempt of the usual and eco guided clinical practice.

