It is considered a clinically relevant difference the successful venous cannulation at the first attempt when, not only allows the cannulation at the first attempt of those cases that hypothetically would be observed, but accumulate to those cases that, in a way observed in the literature, the cannulation has been achieved at the second attempt, and hypothetically, that success can be achieved in the first attempt.

The comparative indicators are based on the comparison method and the reduction of intraindividual variability. It is considered a root of the experience, one of them is lost; An average of both percentages has been made, thus obtaining a 12% loss approximately.

Therefore, the calculation of the sample size should be followed through the modality of proportions, paired measures (repeated in a group). Fix in the proportion with pre-intervention event 0.74, in the proportion with post-intervention event 0.95, and the loss ratio 0.12.

Finally, the estimated sample size is 60 subjects.

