14.1.3.1.1. UNIVARIATE STATISTICS

In order to prove the veracity of the following null hypothesis, in the previously calculated sample it will be necessary to use a univariate nonparametric test for related samples; Mc Nemar test.

H0: Successful antebrachial venipuncture at the first attempt is not affected by the use of alternative methods.

H1: Successful antebrachial venipuncture at the first attempt if it is affected by the use of alternative methods.

The alternative methods refer to the interventions mentioned above.

If Mc Nemar's test results in a p-value <0.05 , the null hypothesis can be rejected and the alternative approved. As a consequence, there will be a need to know which alternative method of the three tested is the most effective.

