14.1.3.1.2. MULTIVARIATE STATISTICS

Therefore, it is considered pertinent to perform a logistic regression, multivariate statistics. The primary variable is assumed as the dependent variable and the secondary variables as returnable or explanatory. The primary variable fulfills the requirement of being dichotomous and the return variables assume any type of variable. It is assumed the need to create dummy variables with alternative methods, whose reference will be the comparator.

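### The logistic regression that is to rank the methods treats each subject's two attempts as independent, so some of its standard errors are wrong and part of the own-control precision is lost

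*Combined protocol and SAP*

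**What the plan says.** Section 6.2 describes a crossover in which "each subject is exposed to an intervention, and it is their own control". Each subject therefore contributes two first-attempt outcomes. Section 14.1.2 sizes the trial with a paired-proportions calculation, and section 14.1.3.1.1 tests the global hypothesis with a paired test: "it will be necessary to use a univariate nonparametric test for related samples; Mc Nemar test".

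If that test is significant, the plan still has to find the most effective of the three methods. Section 14.1.3.1.2 gives this to a logistic regression: "The primary variable is assumed as the dependent variable and the secondary variables as returnable or explanatory". It adds dummy variables for the methods with the comparator as reference, so both attempts of every subject enter. It names no subject term, random effect, conditional likelihood, clustering or robust variance.

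Section 14.3 uses the same regression for the effectiveness of all methods, and a logistic regression again for the association of success with demographic characteristics. Blocking is mentioned there only for the hemolysis ANOVA. Section 14.1.3.2.2 asks for an odds ratio for each intervention without saying which model it comes from.

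**The concern.** The main objective (section 5.2.1) is to identify the best method. A McNemar test pooled over the three interventions cannot rank them; only the regression can. The pairing is thus kept in the sample size and the global test, and dropped where the main question is answered.

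As listed, the model treats 2 × 54 = 108 attempts as independent. If a subject who is easy to cannulate once tends to be easy again, three things follow:

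- Intervals for a method against the comparator are too wide.
- Intervals for age, sex, BMI and other subject-level characteristics are too narrow, because each subject is counted twice. This can produce false demographic associations.
- In comparing two interventions, a subject's own comparator result no longer helps to adjust for how difficult that subject is.

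**Working it through.** **Inputs**

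- Rates and losses (section 14.1.2): "Fix in the proportion with pre-intervention event 0.74, in the proportion with post-intervention event 0.95, and the loss ratio 0.12". Two-sided alpha is 5% and power 80%.
- Size: 60 subjects in section 14.1.2, 54 in section 2.13. The envelopes in section 6.3 split subjects equally, so 54/3 = 18 per method against 54 comparator attempts. With 60 subjects (20 and 60) the ratios below are the same.
- Within-subject correlation ρ: not in the documents, so a range is assumed. With s₁s₀ = √(0.95×0.05×0.74×0.26) = 0.0956, the largest value possible at these rates is (0.74 − 0.74×0.95)/0.0956 = 0.387.

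**1. The plan's own figure.** With d = 0.21 and maximum discordance p = 0.26 + 0.05 = 0.31, n = [1.96√p + 0.842√(p − d²)]²/d² = (1.091 + 0.434)²/0.0441 = 52.75. Dividing by 0.88 gives 59.95, that is, 60. The figure is reproduced and rests on a paired calculation.

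**2. One method against the comparator (log odds ratio, 18 v 54 attempts).** True variance = 1/(18 s₁²) + 1/(54 s₀²) − 2ρ/(54 s₁s₀). Ordinary regression omits the last term.

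- At 0.95 v 0.74: 1.1696 + 0.0963 = 1.2658, so the ordinary SE is 1.125. The true SE is 1.108, 1.090, 1.072 and 1.056 at ρ = 0.1, 0.2, 0.3 and 0.387. The ordinary SE is 1.6%, 3.2%, 4.9% and 6.5% too large.
- At 0.74 v 0.74: ordinary SE 0.620; true SE 0.589, 0.555 and 0.519 at ρ = 0.2, 0.4 and 0.6. It is 5%, 12% and 20% too large.

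**3. Subject-level covariates.** A covariate that is equal in both of a subject's records has its variance understated by a factor of about 1 + ρ. The two-sided type I error is then 2[1 − Φ(1.96/√(1+ρ))], which is 7.4%, 9.8% and 12.1% at ρ = 0.2, 0.4 and 0.6.

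**4. Intervention against intervention.** These attempts come from different subjects, so the ordinary SE is about right. Using each subject's own comparator result multiplies the SE by about √(1−ρ²) in large samples: 0.98, 0.92 and 0.80 at ρ = 0.2, 0.4 and 0.6.

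**5. Simulation at the trial's size** (18 pairs per method, no effect, all rates 0.74, 400 runs; GEE without small-sample correction):

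| Contrast | ρ | Ordinary SE | Its actual SD | Ordinary rejection | GEE SD | GEE rejection |
|---|---|---|---|---|---|---|
| Method v comparator | 0.37 | 0.658 | 0.588 | 1.5% | 0.552 | 4.5% |
| Subject-level covariate | 0.37 | 0.236 | 0.291 | 9.3% | 0.289 | 6.8% |
| Subject-level covariate | 0.57 | 0.239 | 0.308 | 11.8% | 0.308 | 7.8% |
| Intervention v intervention | 0.37 | 0.814 | 0.824 | 3.8% | 0.741 | 4.0% |
| Intervention v intervention | 0.57 | 0.825 | 0.760 | 1.3% | 0.648 | 2.3% |

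The precision lost between interventions is 1 − 0.741/0.824 = 10% and 1 − 0.648/0.760 = 15%. Part of the covariate excess is a small-sample effect. With 200 pairs per method and ρ = 0.57, however, ordinary regression still rejects 11.0% and GEE 5.0%.

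**6. Sparse failures.** At 95% success, 18 subjects have no failure with probability 0.95¹⁸ = 0.397. For at least one of three methods the probability is 1 − (1 − 0.397)³ = 0.78. The expected number of failures per method is 18 × 0.05 = 0.9, so the large-sample figures for the planning rates in step 2 are only a guide.

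**The case against.** The best defence has four parts.

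- **The error against the comparator is conservative and small at the planning rates.** This stands. At zero correlation there is no error at all, and the documents give no correlation. A zero correlation would, however, contradict the own-control reason given for the design.
- **The text is silent on a subject term and does not exclude one.** This is true, but the section lists the model terms and none is for the subject. Followed exactly, it gives an unpaired analysis.
- **Clustering alone does not make the model estimable.** This stands. When a method has no failures, neither ordinary logistic regression, GEE nor a random-intercept model gives a finite estimate for it, so a fallback is needed. Separately, section 14.1.1 lists the number of attempts among the secondary variables, and that number determines the outcome. Clustering does not cure this.
- **The regression follows only a significant McNemar test.** This is true of the main analysis and limits the reach of the problem there.

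Two stronger readings are tempting. A reader might infer that every standard error in the regression is wrong, including those between interventions; step 4 shows that those are about right. A reader might also infer that a clustered model would nearly double power against the comparator. The documents give no basis for that. Simulations at rates outside the plan (comparator 60%, method 78%), with the small-sample correction, moved rejection only from about 25% to 27% at correlation 0.2 and from 20% to 26% at 0.41. Heat against pressure showed no useful gain in rejection.

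**Conclusion.** The regression in section 14.1.3.1.2, and its reuse in 14.3, does not match the paired design, sample size and global test. The size depends on an assumed positive within-subject correlation and on both attempts of each subject entering the model:

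- one method against the comparator: SE about 2-6% too large at 74% and 95%, and about 5-20% too large with no effect at correlations 0.2-0.6;
- subject-level covariates: type I error roughly 7-12% instead of 5%;
- intervention against intervention: SE about right, but at this trial's size up to about 10-15% of precision is lost at correlations of about 0.4-0.6, and little at 0.2.

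This should be fixed before analysis. It does not invalidate the trial: the McNemar test keeps the pairing and the 60 subjects are unaffected. The only anti-conservative error falls on a secondary objective.

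**What to change.** In section 14.1.3.1.2 and in both logistic regressions of section 14.3, name one model that accounts for subject. One choice is GEE logistic regression clustered by subject, with exchangeable correlation and a small-sample variance correction. Read all method contrasts and the odds ratios of section 14.1.3.2.2 from that model, and state that they are population-averaged. Do not leave the choice open between GEE and a random-intercept model, because their odds ratios differ in meaning.

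Also name a fallback for a method with no failures: for example, an exact paired McNemar test of each method against the comparator, or a penalised-likelihood fit with subject-clustered variance.

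The cost is wording in the analysis plan, plus a check that the statistical package named in the plan offers the chosen variance correction. No data, visits or subjects are added, and the change should be made before the outcome data are seen.

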4.2. Justification

This study, which precedes the present one, concludes that: the application of this intervention is effective for the exacerbation of antebrachial venous perception, it denotes a characteristic of protection against the consequences that a difficult venous perception entails, thus reflecting a high impact avoidable potential of difficult venous perceptions, and all that this entails. Finally, it reveals that it is possible to benefit from this intervention to the entire population, but it is more fruitful if it is intended for subjects with a compromised venous perception, or with a low stage according to the VIA scale (10,36).

Likewise, the study ends with the need to which it is intended to respond in this protocol: clarify the cause of the finding found; that is, if the increase in antebrachial venous perception is due to exposure to dry heat and / or high stagnation pressure (37).

In the same way, it has been considered that the evaluation of the quality of the blood samples could be justified, in what refers to the intensity of hemolysis. No study has been found that proves, empirically and validly, what both Lundbeg et al. like other authors in the pre-pre-analytical phase; number of attempts in intravenous cannulation, pain and tourniquet aspects with respect to the intensity of hemolysis (25, 26, 28,30).

As a consequence, it has also been considered that the need to design and validate a visual scale of hemolysis could be justified; Detecting the intensity of hemolysis in a precise and valid way.

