7. SELECTION AND WITHDRAWAL OF SUBJECTS

7.1. Sampling and type of population

It is considered a non-probabilistic sample study, for the convenience of healthy volunteers. The existence of the bioequivalence test is communicated and it is the volunteers who come to register their participation for particular reasons, they are easily accessible groups with specific characteristics. In addition, all of them maintain a fast of, at least, 6-8 hours prior to peripheral intravenous cannulation.

All individuals recruited to perform the fieldwork must have met all the inclusion criteria, and none of exclusion.

7.2. Inclusion criteria.

Subjects that meet the following requirements will be included:

- o Age 18 to 55 years old (42).
- o Have signed the informed consent of this essay.

o Participate in a clinical bioequivalence trial of the Clinical Trials Unit of the University Hospital of La Princesa.

o Do not reach stage I on the VIA scale, in the first assessment.

o Fluid intake equal to or less than 500 ml, in the last 6-8 hours before venous drainage (15,38).

The exclusion criterion of VIA stage I scale could be justified as a consequence of the conclusions of the research study that precedes the present one (37).

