9.4. Development of fieldwork of the trial

The first evaluation of the VIA scale (36) will be carried out, according to the number of optimal puncture points (PPO), before the application of the arm assigned by the main researcher and will correspond to the inclusion and exclusion criteria; pre-intervention assessment. This will be transcribed as the first VIA scale assessment (36).

In the interventions, the VIA scale will be evaluated twice (36). The second assessment will be carried out after the application of the intervention or randomly assigned comparator; and before performing venipuncture.

In the case of the comparator, it will only be evaluated once; It will not be assessed if it denotes a change of stage, since no intervention is applied. If this corresponds to the first period, the registration stage of the inclusion / exclusion criteria will be transcribed, if it corresponds to the second period, the corresponding nurse will assess it.

In both cases, the intervention or comparator will be applied, the success or failure in successful venipuncture will be recorded on the first attempt. In the case of failure, the attempt number to which the catheterization was possible will be recorded. Table 2

| ORGANIZATION CHART ACCORDING TO VISITS | | |
|---|-----------------|---|
| ENROLLMENT VISIT | FIRST DAY ENTRY | SECOND DAY ENTRY |
| 
 1. Information Sheet 2. Informed consent form. 3. Training for the nurses listed on the form. | X | 
 1. Subjects inclusión according to inclusión and exclusión criteria VIA assessment 2. Randomized assignment 3. Intervention/comparator assigned application. 4. Post intervention VIA assessment. 5. VAS pain assessment. 6. FITZPATRICK scale skin assessment 7. Hemolysis analysis. |

Table 2. Organization chart according to visits. Own elaboration.

This organization chart, Table 2, will be specific to the first period of the clinical trial. Another detailed organization chart has been prepared for the two study periods in section 9.7.3.

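### The pre-intervention VIA stage is recorded for every subject but left out of the model that ranks the three interventions, at a modest cost in precision

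*Combined protocol and SAP*

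**What the plan says.** Section 9.4 places the first VIA assessment ahead of the assigned arm: "The first evaluation of the VIA scale (36) will be carried out, according to the number of optimal puncture points (PPO), before the application". It is recorded: "This will be transcribed as the first VIA scale assessment". An intervention is followed by a second assessment before the puncture. In a comparator period VIA is taken once: the eligibility value if that is period 1, a fresh nurse assessment if it is period 2. Section 7.2 makes the first value an entry criterion: "Do not reach stage I on the VIA scale, in the first assessment".

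The step meant to find the best method is the logistic regression in 14.1.3.1.2, with dummy variables for the methods and the comparator as reference: "The primary variable is assumed as the dependent variable and the secondary variables as returnable or explanatory". Section 14.1.1 names as secondary variables the number of attempts, hemolysis, pain, Fitzpatrick type and fluid intake. Under the affiliation heading it adds fasting, age, sex, race, blood pressure, heart rate, temperature and BMI. VIA is in neither group, nor in the objectives (5.2.2) or the attached secondary analyses (14.3).

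On the design, section 6.2 states that "all individuals will be subjected to one of the three interventions and the comparator".

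**The concern.** The main objective (5.2.1) and the step after McNemar's test (14.1.3.1.1) both ask which of the three interventions is most effective. McNemar's test compares a subject with himself or herself, so stable vein quality drops out. The ranking has no such protection: heat, pressure and the combination are given to different people, about 20 per arm. The envelopes in 6.3 balance intervention and sequence, not VIA stage. The sentence there that mentions the first VIA evaluation seeks equal numbers per arm, which is not equal stages.

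At stake is some avoidable noise in the ranking, and the loss of a baseline covariate that the sponsor considered important enough to decide eligibility. The same sentence of the plan admits covariates that should not be there, because they are measured after the puncture or determined by it.

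**Working it through.** **The plan's own sample size.** Inputs from 14.1.2: 0.74, 0.95, two-sided 5%, power 80%, loss 12%. Assuming independence within pairs, the discordant proportions are 0.74 × 0.05 = 0.037 and 0.26 × 0.95 = 0.247. So ψ = 0.284 and d = 0.21.

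- n = [1.96√ψ + 0.8416√(ψ − d²)]² / d² = 48.1.
- Continuity-corrected: (n/4)[1 + √(1 + 2/(nd))]² = 52.8.
- Allowing for loss: 52.77/0.88 = 59.97, the stated 60.

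This sizes one paired comparison. Five blocks of 12 with four envelopes per intervention give 20 per arm. With 54 completers there are 18 per arm. At 18-20 per arm, power between two interventions is 41-45% for 0.74 v 0.95 and 17-18% for 0.85 v 0.95.

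**Chance imbalance.** Assumed, because the documents do not say: 30% or 50% of subjects have poorer veins. The exact binomial probability that two given arms differ by at least 20 points in that share is 20-24% with 18 per arm and 23-27% with 20 per arm.

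**Shift caused by a 20-point imbalance.** Two equally effective interventions at 85%; shift = 0.20 × simulated slope of the difference on the imbalance (20,000 trials, 18 per arm).

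| Assumed VIA odds ratio | Slope, 50% poorer | Slope, 30% poorer | Shift (points) |
|---|---|---|---|
| 2 | 0.078 | 0.098 | 1.6-2.0 |
| 4 | 0.156 | 0.193 | 3.1-3.9 |
| 8 | 0.219 | 0.285 | 4.4-5.7 |

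After standardising for VIA the slope is about zero.

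**Ceiling near 95%.** With a 50/50 mix and 95% overall success, the widest possible gap is 100% v 90%, or 10 points. The SD of the imbalance between two arms of 20 is √(2 × 0.25/20) = 0.158. For two arms both at 95%, one SD therefore moves the difference by at most 0.158 × 10 = 1.6 points.

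**Gain in precision.** At 85% and 20 per arm, SE = √(2 × 0.85 × 0.15/20) = 11.3 points. With a 50/50 mix and a gap of 20 or 30 points, the part due to VIA imbalance is 0.158 × 20 = 3.2 or 0.158 × 30 = 4.7 points.

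- √(11.3² − 3.2²) = 10.8, a reduction of about 4%.
- √(11.3² − 4.7²) = 10.2 to 10.3, a reduction of about 9%.

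This ignores the cost of estimating the covariate. In the simulation the SD fell only from 0.118 to 0.115 at odds ratio 8, and at odds ratio 2 it rose slightly (0.120 to 0.122 with 50% poorer veins). The chance of picking the truly best arm (0.95 v 0.85 and 0.85) rose by at most 1.7 points, from 73.8% to 75.5%.

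**Room in the model.** At the planned rates, 54 completers give 54 × 0.26 = 14.0 comparator failures and 54 × 0.05 = 2.7 intervention failures, about 17 in all.

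**Number of attempts.** This variable takes the values 1 to 4. A value of 1 is a first-attempt success and anything higher is a failure. As an explanatory variable it separates the outcome completely.

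**The case against.** Randomisation makes any imbalance in vein quality random, and that imbalance is already inside the ordinary standard error. Excluding stage I narrows the range of veins. The between-arm limit is sample size far more than covariate choice. All of this stands, and it is why the point is about precision.

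A conditional logistic model would remove stable vein quality without any VIA term. That is true, but the plan states no subject term at all. Relying wholly on within-subject differences is also expensive: on the risk scale the simulated SD of an intervention contrast rose from about 0.12 to 0.17-0.19, and some dependence on VIA imbalance remained.

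A reader might infer three stronger things that the documents do not support:

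- **That the ranking is biased.** Nothing in the allocation favours one arm.
- **That shifts of several points should be read against the planned 21-point effect.** That effect is intervention against comparator, and the gaps needed for larger shifts cannot occur in an arm at 95% with an even stage mix.
- **That section 4.2 shows VIA stage modifies cannulation success.** It says of the predecessor's intervention that "it is more fruitful if it is intended for subjects with a compromised venous perception, or with a low stage according to the VIA scale", but the outcome there was venous perception. Section 9.8 only suggests a link to cannulation.

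**Conclusion.** The omission is real: the first VIA stage is collected before any method, decides eligibility, and enters no analysis, while the ranking of interventions is a between-subject comparison. The consequence is a modest loss of precision. The shift of about 2-6 points per 20-point imbalance at 85% success rests on assumed odds ratios of 2-8 and an assumed 30-50% with poorer veins. The 4-9% reduction in standard error rests on an even stage mix and a 20- to 30-point gap in success, and is before the cost of estimating the covariate. The stated 60 subjects is unaffected. The change is still worth making because the value is already collected, and because naming it in advance avoids a later charge of selective adjustment. Removing number of attempts from the explanatory set matters whatever is assumed about VIA.

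**What to change.** - In 14.1.1, list the first VIA stage (pre-intervention, period 1) as a baseline variable. Say explicitly that the assessment made after an intervention and the period 2 assessments are not used for adjustment.
- In 14.1.3.1.2, pre-specify it as a single ordinal or two-level covariate in the model comparing the interventions.
- Fit that model with a term for subject, as a mixed model or by GEE, since each subject contributes two observations. A purely conditional model cannot estimate a VIA main effect.
- Remove number of attempts, pain and hemolysis from the explanatory variables.
- Label any VIA-by-method interaction exploratory.

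The cost is SAP wording. Section 9.4 has the value transcribed; the case report form is not shown, so confirm that it has a field for it. The downside is one more parameter with about 17 expected failures, offset by the three variables that leave the model.
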